6.7.2.1.5. Population summary for treatment comparison

The hazard ratio and its corresponding 95% CI will be presented. P-value from stratified Logrank test will also be presented.

All time-to-event analyses will include data collected in the double-blind period. The stratified Cox proportional hazard model including baseline FVCpp stratified by randomization stratification factor will be used to estimate the hazard ratio and its corresponding 95% CI. A stratified log-rank test stratified by randomization stratification factor will be used for treatment comparison.

For time from randomization to the first acute IPF exacerbation, all events pre-defined in the adjudication charter will be adjudicated by an independent Adjudication Committee. The adjudicated results will be summarized by categories of confirmed, suspected, or not acute respiratory exacerbation.

In addition, all acute respiratory exacerbations will be further summarized as:

- a triggered acute respiratory exacerbation
- an idiopathic acute exacerbation (i.e., no trigger identified).

6.7.2.2. Continuous Endpoints with MMRM Model

6.7.2.2.1. Estimand Strategy

Same as Section 6.7.1.1.1

6.7.2.2.2. Population of Interest

Same as Section 6.7.1.1.2

Confidential Page 29 of 56

6.7.2.2.3. Intercurrent Event Handling Strategy

Same as Section 6.7.1.1.3

For all post-death analysis visits, the missing values will be set as the worst observed post-baseline values (lowest FVCpp and LCQ score, highest QLF, UCSD-SOBQ, and SGRQ score) across all subjects in the double-blind period. Study day will be imputed as the target day of the corresponding analysis visit.

6.7.2.2.4. Analysis Variables

6.7.2.2.4.1. Change from baseline in QLF volume

The Quantitative Lung Fibrosis (QLF) volume is calculated as *QLF=total lung capacity volume* (TLC) * % of quantitative lung fibrosis for fibrosis of the whole lung.

6.7.2.2.4.2. Absolute change from baseline in FVCpp

The absolute change from baseline in FVCpp is derived with the formula below:

FVCpp value at Post baseline visit - FVCpp value at Baseline

6.7.2.2.4.3. Relative change from baseline in FVCpp

The relative change (%) from baseline in FVCpp is the change from baseline FVCpp value as a percentage of the baseline FVCpp value and is derived with the formula below:

$$\frac{FVCpp \ value \ at \ Post \ baseline \ visit - FVCpp \ value \ at \ Baseline}{Baseline \ FVCpp \ value} \times 100$$

6.7.2.2.4.4. Change from baseline in SGRQ

Refer to Appendix 3 for details of scores for St. George's Respiratory Questionnaire (SGRQ). The total score of SGRQ together with the symptom, activity, and impact domain scores, will be included in the analysis.

6.7.2.2.4.5. Change from baseline in the total score of UCSD-SOBQ

Refer to Appendix 4 for details of scores for University of California, San Diego – Shortness of Breath Questionnaire (UCSD-SOBQ).

6.7.2.2.4.6. Change from baseline in LCQ

Refer to Appendix 5 for details of scores for Leicester Cough Questionnaire (LCQ). The total score of LCQ together with the physical, psychological, and social domains cores, will be included in the analysis.

6.7.2.2.5. Population Summary for Treatment Comparison

Treatment difference of LSMeans (and SE) at each scheduled visit and the corresponding 95% CI will be presented.

Confidential Page 30 of 56

All post-baseline visits for the specified parameters below during the double-blind period will be included in the analysis. Change from baseline for the specified endpoints (excluding baseline visits) will be analyzed using a Mixed Model for Repeated Measures (MMRM) approach with fixed effects for treatment, visit (as a factor), treatment-by-visit interaction, randomization stratification factor, and covariates (baseline values, sex, age, race group, and height). Covariates of sex, age, race group, and height will be excluded from the model for FVCpp since these variables have already been adjusted in the definition of FVCpp.

6.7.2.3. Subgroup Analysis for Secondary Efficacy Endpoints

The same subgroup analysis defined in Section 6.7.1.4 will be performed for all secondary efficacy endpoints.

6.8. Safety Analysis

The safety analyses will be performed for the SAF.

6.8.1. Adverse Events (AEs)

Adverse events will be coded using MedDRA.

A new or worsening AE occurring on or after the first dose of study drug and within 60 days after the last dose of study drug is defined as a treatment-emergent adverse event (TEAE). AEs that started after 1st dose in the OLE period will be excluded from the main study. Partially or incompletely missing AE start/stop date/time will be imputed (Appendix 1).

If more than one event occurs with the same system organ class (SOC) and preferred term (PT) for the same patient, the patient will be counted only once for that preferred term using the most severe and most related occurrence for the summarization by common terminology criteria for adverse events (CTCAE) severity grade and relationship to the study treatment. Relationship to study treatment will be imputed as "Related" for any TEAE with a missing value for relationship.

The cumulative incidence of the following AE categories including the number (%) of subjects will be produced:

- Summary of all AEs
- TEAEs by PT
- TEAEs by SOC and PT
- TEAEs by SOC, PT, and maximum severity
- TEAEs by SOC, PT, and investigator-determined relationship
- TEAEs with severity grade \geq 3 by SOC and PT
- TEAEs related to study treatment determined by the investigator by SOC and PT
- TEAEs with frequency \geq 5% of subjects in either treatment arm by SOC and PT

Confidential Page 31 of 56

- Non-serious TEAEs with frequency ≥ 5% of subjects in either treatment arm by SOC and PT (Note: this is required for ClinicalTrials.gov)
- TEAEs leading to discontinuation of study treatment by SOC and PT
- TEAEs leading to interruption of study treatment by SOC and PT
- Treatment-emergent serious AEs (TESAEs) by SOC and PT
- TESAEs by PT
- TESAEs by SOC, PT, and maximum severity
- TESAEs related to study treatment determined by the investigator by SOC and PT
- Fatal TESAEs (i.e., adverse events that have an outcome of death) by SOC and PT
- All-cause deaths

Listings of all adverse events, TESAEs, TEAEs leading to study treatment discontinuation, TEAEs leading to death, and all-cause deaths will be provided.

In addition, TEAEs and TESAEs will be presented by subgroups as described in Section 6.7.1.4 along with an additional subgroup assessment by concomitant steroid medication use.

6.8.2. Special Safety Events

Treatment-emergent special safety events including:

- 1. Hypersensitivity (any time)
- 2. Infusion reactions (occurred on the day or the day after any study drug infusion)
- 3. Anaphylactic reactions (occurred on the day or the day after any study drug infusion)

Items 1 and 2 include both hypersensitivity and angioedema events. Both items 1 and 2 will be listed and summarized similarly to TEAEs:

- Events by event type, SOC, PT, and maximum severity
- Events by event type, SOC, PT, and subgroups (same as TEAEs)

Item 3 will be listed and summarized by PT only.

The preferred term list for these special safety events will be finalized prior to database lock.

6.8.3. Clinical Laboratory Parameters

Descriptive statistics for laboratory values (in SI units) and changes from baseline at selected visits will be presented for the following laboratory parameters. The number (%) of subjects by toxicity grades at selected visits will also be provided for selected lab tests. Shift tables for selected parameters from baseline to worst post-baseline will be provided.

Confidential Page 32 of 56

Table 4: Laboratory Tests

Hematology Panel:	Chemistry Panel:
Absolute neutrophil count (ANC), Basophils, Eosinophils, Erythrocyte count (RBC), Hematocrit %, Hemoglobin, WBCs (Leukocyte count), Lymphocytes, Mean corpuscular volume, Monocytes, Neutrophils, Platelets	Bicarbonate, blood urea nitrogen (BUN), Calcium, Creatinine, Chloride, Magnesium, Glucose, ALP, ALT, AST, total Bilirubin, Albumin, Phosphorous, Potassium, Sodium, Cholesterol, Total Protein, GGT, Triglycerides
Coagulation Panel: International Normalised Ratio (INR), partial thromboplastin time (aPTT/PTT)	

6.8.4. Liver Function Tests

Liver function test results and the number (%) of subjects above 2×ULN or 3×ULN will be summarized over selected visits.

A matrix scatter plot of liver enzymes and bilirubin showing the maximum ALT or AST vs. total bilirubin during treatment on natural-log scales with a dotted line drawn at 3×ULN for ALT or AST vs. at 2×ULN for total bilirubin will be provided.

6.8.5. Vital Signs

Heart rate (beat/min), diastolic and systolic blood pressure (mmHg), temperature (°C), and body weight (kg) will be descriptively summarized by treatment at selected visits.

Vital sign values are potentially clinically significant (PCS) if they meet both the observed value criteria and the change from baseline criteria listed in Table 5 below. The number and percentage of subjects with post-baseline PCS values will be tabulated by treatment group. The percentages are to be calculated relative to the number of subjects with baseline and at least one post-baseline assessment. The numerator is the total number of subjects with at least one post-baseline PCS vital sign value. A supportive listing of subjects with post-baseline PCS values will be provided including the patient ID, study center, baseline, and post-baseline values. A listing of all AEs for subjects with PCS vital signs will also be provided.

Confidential Page 33 of 56

Wital Sian Danamatan	Ela a	Criteria*		
Vital Sign Parameter	Flag	Observed Value	Change from Baseline	
Systolic Blood Pressure (mmHg)	High	≥ 170	Increase of ≥ 20	
	Low	≤ 90	Decrease of ≥ 20	
Diastolic Blood Pressure (mmHg)	High	≥ 110	Increase of ≥ 15	
	Low	≤ 45	Decrease of ≥ 15	
Heart Rate (bpm)	High	≥ 120	Increase of ≥ 20	
	Low	≤ 50	Decrease of ≥ 20	
Weight (kg)	High	-	Increase of ≥ 10%	
	Low	-	Decrease of ≥ 10%	

Table 5: Criteria for Potentially Clinically Significant Vital Signs

6.8.6. Electrocardiogram (ECG)

ECG results (normal, abnormal-clinically significant, and abnormal-not clinically significant) will be summarized by treatment over visits. A shift table for ECG from baseline to worst post-baseline will be provided.

6.8.7. Physical Examination (PE)

Abnormal PE results will be summarized by treatment over visits. A shift table will be provided if data is appropriate. A listing of abnormal PE results will be provided.

6.8.8. Pregnancy Test

Pregnancy tests for women of childbearing potential (WOCBP) only: serum pregnancy test at Screening; urine pregnancy tests (pre-dose) during study visits.

A listing of positive pregnancy test results during study visits will be provided.

6.9. Biomarker Endpoint Analysis

All analyses for the exploratory biomarkers listed in Section 4.5 will be performed for the SAF based on observed data as appropriate. Descriptive summaries will be performed for the other exploratory biomarkers as appropriate.

A listing will be provided for Tryptase at the time of any suspected hypersensitivity/ anaphylactic reactions, as defined in the protocol.

6.10. Immunogenicity Analysis and PK

Summary of immunogenicity data will be based on IGS and listings will be on SAF. The analysis dataset and data listing will include all available anti-drug antibody (ADA, also named HAHA) samples. The following terms and definitions are implemented.

Confidential Page 34 of 56

^{*}Except for body weight, a post-baseline value is considered as a PCS value if it meets both criteria for observed value and change from baseline.

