6.2.4.2.3. Suspected Hypersensitivity or Anaphylactic Reactions

Any immunogenic reactions, including drug-related hypersensitivity or anaphylaxis, should have PK, HAHA, HAHA-NA, CTGF and tryptase drawn within 24 hours of a suspected reaction from pamrevlumab (see **Appendix 2** for more detail). This is in addition to timepoints in which PK, HAHA, and HAHA-NA and CTGF were drawn pre-infusion and post-infusion.

This will not be considered optional for the subject unless there is local institutional guideline consideration for total blood volume collection on the same day as a standard blood draw timepoint, which could preclude the subject from having this collection take place within 24 hours. The Tryptase sample should be drawn within 1 to 6 hours of immunogenic reaction, and all other samples should be collected within 24 hours of the immunogenic reaction. See **Appendix 2** for more detail.

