APPENDIX 2. PHARMACOKINETIC, BIOMARKER, IMMUNOGENICITY AND GENOMICS SAMPLING

Timepoint ^a	PK ^g (Plasma)	Biomarkers ^{b,f} (Serum and plasma)	CTGF ^b (Plasma)	HAHA/HAHA-NA ^e (Plasma)	Genomics ^{b,g} (Whole blood)	Tryptase (serum)
Day 1	X ^c	X	X	X ^b	X	
Day 8	X ^d					
Day 15	X ^d					
Week 3	X ^c					
Week 12	X ^c					
Week 24	X ^c	X	X	X ^b		
Week 36	X ^c		X	X ^b		
Week 48 /Last dose/ET	X ^c	X	X ^e	X ^b		
28 days after Last dose	X ^d	X	X ^f	X ^b		
Suspected Hypersensitivity/ Anaphylactic Reaction	X ^h		X ^h	X ^h		X ^h

Abbreviations: PK = Pharmacokinetic; CTGF = connective tissue growth factor; HAHA = human anti-human antibody; HAHA-NA = human anti-human antibody neutralizing antibody; ET = Early Termination

a.) For all time points, the actual date and time of sample collection must be recorded, in addition to date and time of study treatment administration.

b.) Sample should be collected within 2 hours prior to dosing start.

c.) Both pre-dose and post-dose samples are required for PK. Pre-dose sample collection should be within 2 hours prior to dosing and post-dose should be between 1-4 hours after dosing end.

d.) Only one sample is required. A ± 2 day window may be applied to the Day 8 and 15 sample.

e.) Samples with positive HAHA results will be tested for neutralizing antibody (HAHA-NA).

f.) Biomarkers will be collected in countries where the Regulatory Agencies allow collection of these samples.

g.) PK and DNA samples will be collected for subjects who consent, except in countries where the Regulatory Agencies do not allow collection of these samples

h.) In the event of a suspected hypersensitivity/anaphylactic reaction, PK, HAHA, HAHA-NA, CTGF and tryptase samples should be collected. The Tryptase sample should be drawn within 1 to 6 hours of immunogenic reaction, and all other samples should be collected within 24 hours of the immunogenic reaction.

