5.5. Analysis Visit Window

Analysis visits, instead of the nominal visits from case report form (CRF), derived from visit dates and visit time windows will be used in the by-visit analyses. Unscheduled visits within a visit window (defined in Appendix 2) will be grouped into the closest scheduled visits based on the visit date. For subjects who have more than one measurement at a certain analysis visit, the last measurement will be used, with the following exceptions:

- Liver function tests, such as Alanine Aminotransferase (ALT), Aspartate Aminotransferase (AST), Gamma-Glutamyltransferase (GGT), Alkaline Phosphatase (ALP), and total bilirubin, in which the maximum value will be used.
- Spirometry data: the best value to be used for analysis as defined in Section 5.1.4.
- Vital signs: the values on the infusion days will be used if applicable.
- ADA assessment: select in the order of 1) last ADA+ assessment; 2) earlier ADA+ assessment; 3) last ADA- assessment.

Confidential Page 19 of 56

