6.10.1.2. Subject ADA Status

- Baseline ADA-positive subject: A subject with a baseline ADA-positive sample.
- Baseline ADA-negative subject: A subject with a baseline ADA-negative sample.
- ADA-positive subject: An evaluable subject with at least one treatment-emergent ADA-positive sample at any time during the study.
- Neutralizing-positive: At least one treatment-emergent ADA-positive sample with neutralizing antibodies detected (if available).
- ADA-negative subject: An evaluable patient without a treatment-emergent ADA sample during the study.
- **ADA**-unknown: Patients without evaluable baseline and/or post-baseline ADA samples will be categorized as "ADA-unknown".

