6.10.3.2. Safety and Efficacy

• AEs and the primary efficacy endpoint will be summarized by ADA status (details in Section 6.7.1.4 and Section 6.8.1).

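### HAHA samples triggered by a suspected reaction count towards ADA status, so tables of reactions by ADA status can show an association when there is none

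*SAP*

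**What the plan says.** **Protocol.** Section 6.2.4.2.3 says that immunogenic reactions "should have PK, HAHA, HAHA-NA, CTGF and tryptase drawn within 24 hours of a suspected reaction from pamrevlumab", and that this is extra to the schedule: "This is in addition to timepoints in which PK, HAHA, and HAHA-NA and CTGF were drawn pre-infusion and post-infusion". Appendix 2, note h, repeats it: "In the event of a suspected hypersensitivity/anaphylactic reaction, PK, HAHA, HAHA-NA, CTGF and tryptase samples should be collected". The scheduled post-baseline HAHA samples in Appendix 2 are Week 24, Week 36, Week 48/last dose/ET, and 28 days after the last dose.

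**Double-blind SAP, ADA status.** Section 6.10 states: "The analysis dataset and data listing will include all available anti-drug antibody (ADA, also named HAHA) samples". Section 6.10.1.2 defines an ADA-positive subject as "An evaluable subject with at least one treatment-emergent ADA-positive sample at any time during the study". Neither section distinguishes a reaction-triggered sample from a scheduled one.

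**Double-blind SAP, use of ADA status.** Section 6.10.3.2 states: "AEs and the primary efficacy endpoint will be summarized by ADA status". Section 6.8.2 tabulates hypersensitivity events and infusion reactions by the TEAE subgroups. Section 6.8.1 takes those subgroups from Section 6.7.1.4, where ADA status is one of them. Anaphylactic reactions, the third special-event category, are listed and summarised by preferred term only.

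**Double-blind SAP, visit windows.** Section 5.5 replaces nominal visits with windows and moves unscheduled samples to the nearest scheduled visit. When a window holds several ADA results, the rule is to "select in the order of 1) last ADA+ assessment; 2) earlier ADA+ assessment; 3) last ADA- assessment". Table 13 sets Week 24 as Days 2 to 211, Week 36 as Days 212 to 295, and Week 48 from Day 296. It has no row for a suspected reaction.

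**The concern.** In a table of reactions by ADA status, ADA status is the exposure and the reaction is the outcome. Here the outcome itself prompts another measurement of the exposure. Under a rule that one positive is enough, more measurements mean a higher chance of being classed as exposed. Part of any excess of reactions among ADA-positive subjects could then reflect extra testing, and the planned tables give no way to separate that part out.

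The schedule adds to this. No post-baseline HAHA sample is scheduled before Week 24. Among subjects still in the study, an antibody that appears and clears in the first months will normally be found only in someone who had a suspected reaction. A triggered sample can also be the single post-baseline result that makes a subject evaluable under Section 5.2.4.

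The second issue concerns by-visit prevalence (6.10.2.1) and the timepoint incidence and titre plots (6.10.2.2). A positive sample drawn at a Week 3 reaction would be reported as a Week 24 result, displacing a negative sample actually drawn at Week 24.

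**Working it through.** The documents state no ADA rate and no reaction rate, so there is no plan figure to reproduce. The rules fix the direction. The size needs assumptions.

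**Scheduled post-baseline samples, k (current protocol)**
- k = 4 for subjects not entering the OLE (Appendix 2).
- k = 3 in the double-blind period for OLE entrants, because their 28-day visit follows the last OLE dose (Appendix 1, note r).
- k = 2 for subjects who withdraw before Week 24. They are due an ET sample and a 28-day sample and cannot enter the OLE (Section 4.4, Appendix 2).

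**Direction.** Let p be the assumed probability that a sample is positive, independent of reactions and of other samples.

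P(ADA-positive, no reaction) = 1 − (1 − p)^k

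P(ADA-positive, one triggered sample) = 1 − (1 − p)^(k+1)

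The difference is p(1 − p)^k, which is never negative. An extra sample can add a positive but cannot remove one.

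**Size with no true association** (without reaction → with one triggered sample, ratio)

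| k | p = 2% | p = 5% | p = 10% |
|---|---|---|---|
| 4 | 7.76% → 9.61%, 1.24 | 18.55% → 22.62%, 1.22 | 34.39% → 40.95%, 1.19 |
| 3 | 5.88% → 7.76%, 1.32 | 14.26% → 18.55%, 1.30 | 27.10% → 34.39%, 1.27 |
| 2 | 3.96% → 5.88%, 1.49 | 9.75% → 14.26%, 1.46 | 19.00% → 27.10%, 1.43 |

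**In the table itself.** Assume also that 5% of subjects react, with k = 4 and p = 5%.
- Among ADA-positive subjects: 0.05 × 0.2262 / (0.05 × 0.2262 + 0.95 × 0.1855) = 6.0%.
- Among ADA-negative subjects: 0.05 × 0.7738 / (0.05 × 0.7738 + 0.95 × 0.8145) = 4.8%.
- The apparent risk ratio is 1.27, with no true association.

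**Persistence.** Let a share f of antibody be persistent, so that every sample from a subject gives the same result. Then P(ADA-positive) = f·p + (1 − f)·[1 − (1 − p)^k].
- f = 0.5, p = 5%: 11.77% → 13.81% for k = 4 (ratio 1.17), and 9.63% → 11.77% for k = 3 (ratio 1.22).
- f = 1 with complete sampling: ratio 1.00.

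**Repeated reactions.** With two triggered samples and p = 2%, the ratio is 1.47 for k = 4 and 1.63 for k = 3.

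**By-visit displays.** A sample from a Week 3 reaction falls on about Day 22, inside Days 2 to 211. The scheduled Week 24 sample has target Day 169, in the same window. If the first is positive and the second negative, Section 5.5 selects the first. No calculation is needed.

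**The case against.** **All samples is a defensible choice for a safety table.** The triggered draw was added in Amendment 2.0 to meet regulatory recommendations on immunogenicity testing. Dropping it from the table would class a subject whose antibody was found at the reaction, and nowhere else, as an ADA-negative reactor. That could hide a real signal. This stands, and it is why scheduled-only status should not replace the all-samples version.

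**Follow-up may not be equal.** Subjects with reactions may stop early. At p = 5%, a reactor with two scheduled samples and one triggered sample has a 14.3% chance of being ADA-positive, against 18.5% for a non-reactor with four: ratio 0.77. On scheduled samples alone it would be 9.75% against 18.5%: ratio 0.53. This also stands. The direction is fixed only for equal follow-up, and the scheduled-only version is not clean either.

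**The effect may be small or absent.** Persistent antibody removes it. Reactions before Amendment 2.0 may have no triggered sample. Hypersensitivity is tabulated from a preferred-term list, so not every tabulated event need have prompted a draw. These limits reduce the size but do not correct the rule.

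**The data can be inspected.** Listings of all ADA assessments (6.10.2.1) and of tryptase (6.9) are planned. They help with individual cases but do not correct a summary table.

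**The by-visit effect is narrow.** It needs a triggered positive and a negative scheduled sample in the same window. Subject-level maximum titres do not depend on the windows. Both statements are correct.

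**Conclusion.** The point holds as a matter of unequal ascertainment. For subjects with equal follow-up, the all-samples rule can only push the tables of hypersensitivity, infusion reactions and AEs by ADA status towards an association. Under independent detection at an assumed 2% to 10% per sample and one triggered draw, the ratio of ADA-positive probability is 1.19 to 1.24 with four scheduled samples and 1.27 to 1.32 with three. For early terminators with two it is 1.46 at 5%. It falls to 1.00 with fully persistent antibody and complete sampling. The documents do not say where in this range the trial lies. The mixing of scheduled and event-driven samples in by-visit displays follows from the SAP's rules whatever the rates.

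Four stronger inferences are not supported:
- A reader might conclude that the tables will link reactions to antibodies by construction. They can do so, but a null effect is within the range.
- A reader might compute a ratio near 2 from a single scheduled sample. Even early terminators are due two under the current schedule, so that figure needs missed samples.
- A reader might extend the point to the anaphylactic-reaction summary. It is by preferred term only and is not affected.
- A reader might extend it to efficacy by ADA status. Nothing here shows that a triggered sample biases the FVC comparison.

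The point does not touch the primary analysis, and it does not apply to the OLE SAP, which rules out subgroup analysis by ADA status.

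**What to change.** 1. Add a flag to the ADA dataset for HAHA samples drawn because of a suspected reaction.
2. In SAP Section 5.5 and Table 13, exclude flagged samples from by-visit prevalence, incidence and titre displays. Give them a separate suspected-reaction timepoint, and list them beside the tryptase and PK results from the same draw.
3. For the hypersensitivity, infusion-reaction and AE tables by ADA status (6.8.1, 6.8.2, 6.10.3.2), present two versions side by side: all samples, and scheduled samples only. In the second, a subject should need at least one scheduled post-baseline sample to be evaluable. State in the SAP and in the table footnote that the all-samples version has unequal ascertainment.
4. Leave efficacy by ADA status as planned.

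The cost is a data flag, a few sentences of SAP text and one extra set of tables. The scheduled-only version misses antibody seen only at the reaction and can be distorted if subjects with reactions stop early. The all-samples version has the extra-testing problem. Neither is sufficient alone, which is the reason for showing both.
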